4.3 JUSTIFICATION FOR INTERVENTION

Bridging disparities in mental health care with technology. Using digital CBT, we can now deliver high-quality, evidence-based behavioral mental health treatment that can be scaled to reach patients in under-resourced settings. Digital CBT has long been shown to be effective in white populations. More recently, we have shown digital CBT is effective for minorities. We found that digital CBT led to significant decrease in depressive symptoms among African American primary care[43, 44] and SCD patients.[45] Our group has also implemented digital CBT for pain with African American children and adolescents with SCD.[46] Thus, there is ample evidence that digital CBT is ready for implementation in SCD clinics and potentially, through community-

based organizations (CBOs) via social media and the Web, creating widespread access to mental health care.

Gap in evidence. No studies have demonstrated the successful implementation and sustainable delivery of a digital CBT service in SCD or any other underserved population in under-resourced settings. This is in part because, despite promising evidence supporting the use of digital CBT for mental health, attrition and poor adherence with this mode of intervention are common.[47] Moreover, engagement with digital interventions may be especially problematic for minority users. Our work shows that African Americans are even less likely than whites to stick with digital CBT programs. African American primary care patients enrolled in our digital CBT trial were less likely than whites to start the program (75% vs. 87%) and to complete all 8 modules (29% vs. 43%). In our pilot study with SCD adults, although patients reported benefits from digital CBT, the average user completed only 3 of 8 possible sessions. Post-study interviews and a focus group revealed that while SCD patients did indeed feel the CBT skills were useful, the content was often not relevant or relatable and did not represent their real-world cultural and health experience. In addition, interventions with this population have to address cultural stigma, a wellknown barrier to recruitment and retention of racial/ethnic minorities in mental health programs. To advance the field, we need innovative approaches to remediating these barriers to the provision, receipt, and benefit of digital CBT-based mental health services in low-resource settings

4.4 END-OF-STUDY DEFINITION

Patients are considered to have completed the study once they have participated in weekly check-ins with a health coach during the 4 weeks and completed the assessments (STIG-9, SCSES, PROMIS, ASCQ-ME, PHQ-9, GAD-7) at the scheduled time points.

5 STUDY POPULATION

5.1 INCLUSION CRITERIA

To be eligible for the study, patients must:

- be between 16 and 35 years of age
- have a diagnosis of SCD (any genotype)
- report significant depression or anxiety symptoms (i.e., Patient Health Questionnaire [PHQ-9] or Generalized Anxiety Disorder Scale [GAD-7] > 4).

5.2 EXCLUSION CRITERIA

Patients are ineligible if they:

- Are unable to read English or understand the consent process
- Are cognitively impaired adults as determined by their treating physician
- Have any condition that in the opinion of the investigator would not allow the patient to continue on the study

5.3 LIFESTYLE CONSIDERATIONS

N/A

5.4 SCREEN FAILURES

Potential participants will be screened for eligibility prior to enrolling into the study. A de-identified log that includes all screenings, study eligibility and consent will be completed by the research coordinators obtaining consent.

5.5 STRATEGIES FOR RECRUITMENT AND RETENTION

At each participating clinical site (Pediatric and Adult SCD Clinics), we will use electronically-administered screening tools, medical record screening and if available, best practice alerts, to identify patients with SCD who have high risk for mental health disorders as indicated by self-report. Best practice alerts will flag patients with a history of mental health diagnosis or who have been prescribed psychopharmacological medication for mental health. In addition to recruitment in the local clinics, potential participants may be recruited through community-based organization websites, social media groups, email listservs, and patient/family meetings. The community-based organization websites are: Sickle Cell 101 (<https://www.sc101.org/>) and Children's Sickle Cell Foundation (<http://cscfkids.org/>).

We have access to these organizations because Sickle Cell 101 and Children's Sickle Cell Foundation are investigators/consultants on the grant that funds this project.

Electronic Screening and Consent Tool. Interested patients will access a short online screener on any mobile device (a compatible smartphone device is necessary to participate; loaner devices will be provided as needed). To be eligible, potential participants must be able to read the study consent and correctly answer comprehension questions; our group is currently using

and has published data on this electronic consent process in a clinical study and a large multisite trial of digital CBT.

Compensation

Due to COVID-19, focus groups will be remote. Remote focus group participants will receive a \$30 grub hub gift card in lieu of food provided at in person focus groups.

If randomized to one of the intervention arms, participants will receive compensation in the form of \$50 for the baseline assessment and starting the CBT program. Then participants will be compensated \$50 for completion of the 1-month follow-up assessment period for a total up to \$100. Also, travel and parking reimbursement may be received for the amount of \$10 for each study-related visit, if applicable.

5.6 RECRUITMENT PLAN FOR PROSPECTIVE STUDIES

Review of study enrollment accuracy will be collected twice weekly by research staff and evaluated quarterly by the principal investigator.

The principal investigator, collaborators, and the research staff will meet on a monthly interval to re-evaluate study goals, subject recruitment, data coding and retention, documentation and identification of adverse events, complaints, and confidentiality of subjects. There will be an evaluation of the progress of the research study, including assessments of data quality, time lines, participant recruitment, accrual, and retention. If recruitment is below 50% of projected within the first 3 months of the study, the principal investigator will suggest a conference call for the study investigators to discuss methods of improving recruitment, including expanding the age inclusion criteria.

6 STUDY INTERVENTION(S) OR EXPERIMENTAL MANIPULATION(S)

6.1 STUDY INTERVENTION(S) OR EXPERIMENTAL MANIPULATION(S) ADMINISTRATION

6.1.1 STUDY INTERVENTION OR EXPERIMENTAL MANIPULATION DESCRIPTION

Each of the 40 participants recruited will be asked to complete one of two CBT programs through a digital mobile app. Participants will only have access to the content within their assigned program.

Both programs will provide users with brief skill building modules and CBT and dialectical behavioral therapy techniques such as relaxation, behavioral activation, distress tolerance, cognitive reframing, and mindfulness meditation, for depression and anxiety. However, one group will use standard engagement methods; the other group will focus on delivering CBT in a culturally sensitive manner specific to African Americans.

6.1.2 ADMINISTRATION AND/OR DOSING

For at least 4 weeks, participants will engage in one of two CBT programs administered through a digital mobile app. Participants will be asked to interact with their assigned program at least once per week, if not more. Both programs will provide participants with brief 5-10 minute skill building modules. In addition to the app-delivered content, participants will also receive weekly (more frequent if requested or needed) follow-up with a health coach. Health coach sessions will reinforce CBT content and encourage participant completion of modules for at least 4 weeks.

All participants will complete short surveys each week they are in the study. These surveys will be sent to their mobile phone as a web URL link. Each week, participants will complete a depression (PHQ-9) and anxiety (GAD7) symptoms questionnaire. At 1 and 4 weeks only, participants will also complete measures of Self-efficacy (SCSES), stigma, pain interference (PROMIS), and quality of life (ASCQ-ME).

6.2 FIDELITY

6.2.1 INTERVENTIONIST TRAINING AND TRACKING

To maintain intervention continuity and fidelity, before any new content is uploaded to the platform it will undergo a review. No new content will be implemented without consensus of the core Pitt and UPMC Health Plan investigators. Effectiveness of all digital content will be evaluated by number of user views, “likes,” and activity subsequent to viewing the content. These metrics are also used in an algorithm to decide what content to push to the user next.

For Health Coach Training see the Health Coach Protocol in the electronic binder.

6.3 MEASURES TO MINIMIZE BIAS: RANDOMIZATION AND BLINDING

Randomization: Participants will be randomized in an equal fashion (1:1) to both study arms. Random permuted block randomization will be used to create an allocation list that will be integrated within our Web-based data entry system.

Reduce the potential for bias. The introduction to both interventions will look identical and participants will not be told what type of training they are receiving. We will make every effort to mask the intervention type; however, as with all behavioral interventions, completely blinding participants to the intervention is challenging. The investigative team will continue to maintain clinical equipoise regarding the comparative therapeutic merits of each treatment. Randomization will avoid selection bias as well as volunteer or referral bias. A dropout analysis will be carried out to determine the contribution of attrition bias. All outcomes measures will be collected electronically, without an interview, to avoid expectation bias. We have also found this mode of data collection to be superior to assessments by phone for timely follow-up.

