Aim 3: Demonstrate that a population-specific implementation strategy improves engagement with a digital CBT-based mental health service. We will recruit 40 adolescents and young adults with SCD (ages 16-35) and comorbid depression and randomize them to either the off-the-shelf digital CBT program and standard implementation strategy that has no content or references to SCD, chronic pain, or the unique challenges facing minority groups, to adapted digital CBT with a SCD-specific implementation approach.

H1: We hypothesize that participants in the adapted digital CBT arm will complete more modules and have more interaction days with the digital CBT program than participants in the standard digital CBT arm.

General Study Design

There are two intervention groups. Both intervention groups will receive cognitive behavioral therapy (CBT) through a digital mobile app. The program provides users with brief (5-10 minute) skill building modules and CBT and dialectical behavioral therapy techniques such as relaxation,

behavioral activation, distress tolerance, cognitive reframing, and mindfulness meditation, for depression and anxiety. It is for research purposes only.

One group will use standard engagement methods while the other group will focus on delivering the CBT in a culturally sensitive manner specific to African Americans.

Both intervention groups will receive weekly (more frequent if requested or needed) follow-up with a health coach who will reinforce CBT content and encourage session completion for at least 4 weeks. In the adapted digital CBT arm, the health coach will use tailored text messages and multimedia communications.

The program provides users with brief (5-10 minute) skill building modules and CBT and dialectical behavioral therapy techniques such as relaxation, behavioral activation, distress tolerance, cognitive reframing, and mindfulness meditation, for depression and anxiety. It is for research purposes only.

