8.3.2 ANALYSIS OF THE PRIMARY AND SECONDARY ENDPOINT(S)

Primary and Secondary Analyses. We will employ linear regression models for the primary outcome of usage days and the secondary outcome of techniques and sessions completed (Hypothesis 1) as a function of study arm (standard CBT vs. adapted CBT). We will account for multiple observations for each participant by including a random effect for subject. Additionally, baseline variables with clinically meaningful between-arm differences will be included as covariates.

Process evaluation. Change scores, baseline to 4 weeks, perceived stigma, relevance, relatability, will be tested as potential mediating variables. Contrasts will be estimated to assess the impact of standard and adapted CBT intervention on 4-week differences in perceived relevance, relatability, and stigma. We will then test whether lower perceived mental health

stigma and higher perceived program representativeness and relevance in the adapted CBT arm, mediates any observed group differences in engagement and program satisfaction.

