8.3.6 SUB-GROUP ANALYSES

Planned sensitivity analyses to determine the impact of key assumptions. The major assumption is that patients will complete the intervention program to which they are randomly assigned. Although we have implemented several methods to promote engagement and limit dropout (e.g., health coaches[94]), digital interventions often experience high attrition over time with few participants completing all assigned modules.[95] We will track the reasons for non-completion and seek patterns (e.g., moved away, died, started working and became too busy, people with higher cognitive level lost interest) that are amenable to statistical analysis of the missing data. Sensitivity to this assumption can be determined by comparing analysis by three levels of participation in the intervention: enrollment and intervention assignment (Intent-to-Treat), participation in at least half the intervention, and zero participation in the intervention. Propensity score methods could also be used to deal with missing data. We will also test for differences in retention by recruitment site (e.g., community vs. clinical).

The comparative effectiveness trial with two active arms might show that both interventions work moderately well, which means there might not be superiority for the entire population. One intervention might be more suitable for certain subgroups of patients, so our Aim 2 analysis of primary and secondary outcomes by mental health subgroup should provide valuable information on suitability of the intervention for different subgroups.

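### Recruitment source is neither a randomization stratum nor a prespecified covariate in the primary usage-days model; coach assignment is not stated and should be recorded.

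*Combined protocol and SAP*

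**What the plan says.** **Randomization (section 6.3).** "Participants will be randomized in an equal fashion (1:1) to both study arms". The method is permuted blocks: "Random permuted block randomization will be used to create an allocation list that will be integrated within our Web-based data entry system". No stratification factor and no block size are given.

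**Primary model (section 8.3.2).** Usage days are regressed on study arm. The only random term is for the participant: "We will account for multiple observations for each participant by including a random effect for subject". Covariates are chosen by what the data show: "Additionally, baseline variables with clinically meaningful between-arm differences will be included as covariates". No variable is named and no threshold is set for what counts as meaningful.

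**Recruitment source.** Section 5.5 describes recruitment in pediatric and adult sickle cell clinics and adds that "potential participants may be recruited through community-based organization websites, social media groups, email listservs, and patient/family meetings". Source enters the planned analysis once, for retention, in section 8.3.6: "We will also test for differences in retention by recruitment site (e.g., community vs. clinical"). Study site, which is not defined as recruitment source, is a predictor only in the exploratory 12-month utilization models of section 8.3.9.

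**Health coaches.** Both arms have weekly coach follow-up. Section 4.1 adds: "In the adapted digital CBT arm, the health coach will use tailored text messages and multimedia communications". Coach messages are also counted in the engagement outcome (section 2.3.3, study endpoints). The number of coaches, and whether one coach serves both arms, is not stated. Sections 6.2.1 and 7.3 refer to a separate Health Coach Protocol that is not part of these documents.

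**The concern.** Someone approached at a clinic visit and someone who answers a community group's online post may well use an app differently. In a trial of 40, an unstratified list can leave the arms visibly different on such a factor. The plan handles this by looking at the baseline table and deciding then whether to adjust. Because neither the variables nor the threshold is fixed, the primary estimate depends on a judgement made after the data are in. A factor that the plan already intends to examine for retention could be settled in advance at almost no cost.

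The coach question is of the same kind but conditional. Participants of one coach share that coach's skill and responsiveness. If each coach works in only one arm, those shared features become part of the arm difference, and a model without a coach term gives too small a standard error. Aim 3 attributes better engagement to a population-specific implementation strategy, so what is at stake is whether a positive result can be credited to the strategy or only to the strategy as delivered by particular coaches.

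**Working it through.** **1. The plan's own figure.** Section 8.1 gives 20 vs 10 usage days, 80% power and 17 per arm, without SD, alpha or sidedness. Assuming a two-sided 5% test and the normal formula, n per arm = 2(1.96 + 0.84)² SD²/10². Setting n = 17 gives SD = 10.4 (variance about 108.3). So N = 34 can be back-solved but not verified. Attrition: 34/(1 − 0.10) = 38, and 40 are planned. The SD of 10.4 is used below.

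**2. How often would source be imbalanced?** Assume each participant is equally likely to come from clinic or community, blocks of 4, and 20 per arm. The difference in community counts is then the difference of two Binomial(20, 0.5) variables, with variance 5 + 5 = 10. A gap of 20 points is a count difference of 4:
- P(difference ≥ 4) = 0.27
- P(difference ≥ 6, i.e. 30 points) = 0.08

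If instead the community share is fixed exactly, the hypergeometric probability of a gap of at least 20 points is 34% (half community), 30% (30% community) or 23.5% (20% community).

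**3. What would it do to the estimate?** Shift = imbalance × source effect. The source effect is an assumption; the documents give none.
- 0.20 × 5 days = 1 day
- 0.20 × 10 days = 2 days

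The planned difference is 10 days. The standard error with 20 per arm is 10.4 × √(2/20) = 3.29, so these shifts are about 0.3 and 0.6 of a standard error.

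**4. What would it do to the test?** Simulated t-tests with source ignored (10,000 runs each, half community): overall type I error 5.0% for a 5-day and 5.1% for a 10-day source effect. Among trials with a gap of at least 20 points it is 5.6% and 8.5%.

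**5. What does adjustment gain?** With a 50:50 mix, source adds (effect)²/4 to the variance if it is left out:
- 5-day effect, source ignored: √[(108.3 + 6.25) × 2/20] = 3.38
- 10-day effect, source ignored: √[(108.3 + 25) × 2/20] = 3.65
- Source in the model, arms balanced by stratification: √[108.3 × 2/20] = 3.29
- Source in the model, list unstratified: about 3.34

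The gain is small for a 5-day effect and moderate for a 10-day effect.

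**6. Coaches, conditional on assignment.** The ICC and the number of coaches are assumptions. With one coach per arm and 20 participants each, the true variance of the arm difference exceeds the apparent one by (1 + 19·ICC)/(1 − ICC): 1.41, 2.05 and 3.22 at ICC 0.02, 0.05 and 0.10. Dividing the critical value 2.024 (38 df) by the square root of each gives the one-coach row. The other rows are simulations with 40,000 runs.

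| Coach arrangement, ignored in analysis | ICC 0.02 | ICC 0.05 | ICC 0.10 |
|---|---|---|---|
| One coach per arm | 9.6% | 16.6% | 26.6% |
| Two coaches per arm | 6.9% | 10.3% | 15.9% |
| Two coaches, each serving both arms | not run | 4.8% | 4.6% |

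Entries are true error rates of a nominal 5% test. Inflation appears only when coaches are nested in arm. With one coach per arm no sample size helps, because coach and arm are the same variable.

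**The case against.** **Source.** A reader might infer that the primary model ignores recruitment source, or that a surplus of clinic recruits in one arm could by itself produce the hoped-for result. Neither is supported. The covariate clause in section 8.3.2 can admit source, which is known before randomization, and an imbalance of the feared kind is what would trigger it. Chance imbalance is already covered by the error rate of a randomized comparison, and a shift of 1 to 2 days is small against 10. Nor does section 8.3.6 say that clinic and community participants are expected to differ; it says only that retention will be compared. All of this stands. What remains is that the clause is applied after the data are seen, with no named variable and no threshold.

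**Coach.** A reader might also infer that coaches are arm-specific and that the error rate is therefore inflated. The documents do not say so. The sentence on tailored messages fits equally well with the same coaches working in both arms, in which case the check finds no inflation, and the Health Coach Protocol may settle the matter. Adapted coach communication is also part of the strategy under test, so only a coach's individual qualities could confound. This stands too, and it is why the coach part is conditional.

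**Crossing coaches with arm** would remove the problem, but it risks tailored messages leaking into the standard arm and diluting the contrast. It should not be demanded.

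**Conclusion.** The point holds as a modest, inexpensive improvement. Recruitment source is not a stratum and reaches the primary model only through a post hoc judgement. The consequence is chance imbalance: a gap of at least 20 points in about 27% of trials (assuming a 50:50 mix, 20 per arm and blocks of 4) and a shift of 1 to 2 usage days at a 20-point gap (assuming a 5- to 10-day source effect). Overall type I error remains near 5%. Nothing here shows systematic bias from the allocation list.

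The coach part is a request for clarification with a stated consequence. If coaches are arm-specific and clustering is ignored, the nominal 5% test has a true error rate of about 7% to 27% for one or two coaches per arm and an assumed ICC of 0.02 to 0.10. If coaches serve both arms, it is not inflated. The documents do not show which applies.

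**What to change.** 1. **Section 6.3:** generate the permuted blocks separately within recruitment source (clinic vs community).
2. **Section 8.3.2:** name source as a prespecified covariate in the primary usage-days model, included whatever the observed imbalance.
3. **Coach:** state how coaches are assigned and record the coach for each participant.
   - If coaches serve both arms, include coach in the model or in a sensitivity analysis.
   - If coaches are arm-specific, state that coach and arm cannot be fully separated (not at all with one coach per arm) and that the nominal 5% test is then anti-conservative. Limit the conclusion to the program together with its coaches.

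**Cost.** Items 1 and 2 need two lists instead of one and one degree of freedom; the planned retention comparison already requires source to be known. Each list may also end mid-block: with blocks of 4, each can be off by 2, so the final split could be 22 to 18 at worst. Item 3 needs one recorded variable and a sentence or two, plus degrees of freedom equal to the number of coaches minus one if coach is fitted as a fixed effect.
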